10.2.3 ANALYSIS FOR VACCINATED PATIENTS ONLY – CML AND AML

Another secondary endpoint is immune response (as defined in Section 9.6) of WT1-epitope specific T cells in blood and/or bone marrow, using validated assays by ELISPOT and/or ICS and tetramer staining. The proportion of responders in the CML group will be compared with the AML group using Fisher's exact test. This analysis will be repeated for the immune response to DOM and the immune response to DOM specific T cells.

The number of WT1 specific T-cells after peptide challenge to the skin and the number of humoral responses (B-cells) to the vaccine components will be summarised using descriptive statistics (wherever assessments have been feasible). Data on kinetics, duration and level of WT1 CD8 T cell responses will also be collected.

11 REGULATORY ISSUES

11.1 CLINICAL TRIAL AUTHORISATION

This trial has a Clinical Trial Authorisation from the UK Competent Authority the MHRA.

11.2 ETHICS APPROVAL

The trial protocol has received the favourable opinion of the Gene Therapy Advisory Committee.

The trial will be conducted in accordance with the recommendations for physicians involved in research on human subjects adopted by the 18th World Medical Assembly, Helsinki 1964 as revised and recognised by governing laws and EU Directives. Each subject's consent to participate in the trial should be obtained after a full explanation has been given of treatment options, including the conventional and generally accepted methods of treatment. The right of the subject to refuse to participate in the trial without giving reasons must be respected.

After the subject has entered the trial, the clinician may give alternative treatment to that specified in the protocol, at any stage, if they feel it to be in the best interest of the subject. However, reasons for doing so should be recorded and the subject will remain within the trial for the purpose of follow-up and data analysis according to the treatment option to which they have been allocated. Similarly, the subject remains free to withdraw at any time from protocol treatment and trial follow-up without giving reasons and without prejudicing their further treatment.

The investigator must ensure that subject's anonymity will be maintained and that their identities are protected from unauthorised parties. On CRFs subjects will not be identified by their names, but by an identification code. The investigator should keep a subject enrolment log showing codes, names and addresses.

11.3 ETHICAL CONSIDERATIONS

Amendments to the protocol may only be made with the approval of the Chief Investigator, and will be subject to review by GTAC and the MHRA. Written documentation of the approval must be received before the amendment can be implemented.

11.4 CONSENT

Consent to enter the trial must be sought from each subject only after a full explanation has been given, an information leaflet offered and time allowed for consideration. Signed subject consent should be obtained. The right of the subject to refuse to participate without giving reasons must be respected.

After the subject has entered the trial the clinician remains free to give alternative treatment to that specified in the protocol at any stage if he/she feels it is in the subject's best interest, but the reasons for doing so should be recorded. In these cases the subjects remain within the trial for the purposes of follow-up and data analysis. All subjects are free to withdraw at any time from the protocol treatment without giving reasons and without prejudicing further treatment.

The Investigator must also ensure the following points are made:

- The patient must be informed that the study drug is new and that the exact degree of activity is at present unknown, but that treating him will contribute to further knowledge.
- A copy of the written informed consent form will be retained by the patient and the original filed in the Investigator's Site File (unless otherwise agreed that the original will be stored in the patients notes and the copies kept in the ISF)
- An explanation of whom to contact for answers to pertinent questions about the research and research subject's rights, and who to contact in the event of a research-related injury to the subject must be given.

11.5 CONFIDENTIALITY

Subjects' identification data will be required for the registration process. The UoSCTU will preserve the confidentiality of subjects taking part in the trial.

11.6 INDEMNITY

The sponsor of the trial is University Hospital Southampton NHS Foundation Trust. For NHS sponsored research HSG (96) 48 reference no.2 refers. If there is negligent harm during the clinical trial when the NHS body owes a duty of care to the person harmed, NHS Indemnity covers NHS staff, medical academic staff with honorary contracts, and those conducting the trial. NHS Indemnity does not offer no-fault compensation and is unable to agree in advance to pay compensation for non-negligent harm. Ex-gratia payments may be considered in the case of a claim.

11.7 SPONSOR

University Hospital Southampton NHS Foundation Trust, Southampton is acting as the main sponsor for this trial. The UoSCTU has been delegated duties by the Sponsor relating to submissions to regulatory authorities, ICH GCP and phamacovigilance. Other delegated duties will be assigned to the NHS Trusts or others taking part in this trial by means of the site clinical trial agreement.

11.8 FUNDING

Leukaemia and Lymphoma Research Fund, and the Efficacy and Mechanisms Evaluation board of the MRC/DOH are funding this trial.

11.9 AUDITS AND INSPECTIONS

The trial may be subject to inspection and audit by University Hospital Southampton NHS Foundation Trust, Southampton, under their remit as sponsor, the UoSCTU as the Sponsor's delegate and other regulatory bodies to ensure adherence to ICH GCP, Research Governance Framework for Health and Social Care, applicable contracts/agreements and national regulations.

12 TRIAL MANAGEMENT

12.1 TRIAL MANAGEMENT GROUP (TMG) AND DATA MONITORING ETHICS COMMITTEE (DMEC)

TMG

Trial Management Group (TMG) is responsible for overseeing progress of the trial. The day-to-day management of the trial will be co-ordinated through the UoSCTU and oversight will be maintained by the Trial Steering Committee and the Data Monitoring and Ethics Committee.

Listings of AR, AE, SAE and SUSARs will be reviewed every 2 to 3 months jointly by the study team (Trial Management Group to include members of UoSCTU and the clinical and laboratory investigators).

DMEC

A DMEC will be convened on behalf of and with input from the Trial Management Group at regular intervals to review the safety listings and recruitment. AR frequency and type will be collected and presented to the Trial Management Group and the independent DMEC. It will then fall to the DMEC to decide whether there is sufficient reason to suspend or terminate the study.

Additionally the DMEC will evaluate on an ongoing basis whether there is any evidence that the vaccination might disadvantage patients in either cohort of the study and in this case might recommend discontinuation.

Life-threatening vaccination-related toxicity is observed in more than one patient, termination of the trial will be discussed among all collaborators and the trial sponsor.

Unplanned DMEC meetings will be called if required during the study.

12.2 COMPLETION OF THE CRF

Data will be collected and retained in accordance with the Data Protection Act (1988). CRFs will be used to collect the data. The Investigator is responsible for ensuring the accuracy, completeness, legibility and timelines of the data reported in the CRFs. Study documents will be retained in a secure location during and after the trial has finished.

The CRFs must be completed in black ink. Only the Investigator and those personnel authorised by them should enter or change data the CRFs. All laboratory data and Investigator observations must be transcribed into the CRF. ECG, MRI and CT scans must be reported in summary in the CRF. The original reports, traces and films must be retained by the Investigators for future reference.

Vital signs may be collected directly into the CRF.

Corrections can be made only by striking out any errors, with a single stroke, and not by using correction fluid. The correct entry must be entered by the side. The incorrect figure must remain visible and the correction should be initialled and dated by the person authorised by the Investigator to make the correction.

After all the queries have been resolved at the end of the study, the Investigator will confirm this by signing off the CRFs. The original CRFs will subsequently be submitted to the UoSCTU for archiving. The Investigator will receive copies of the CRFs and Data Clarification Forms.

12.3 STUDY PERFORMANCE AND MONITORING

Before the study can be initiated, the prerequisites for conducting the study must be clarified and the organisational preparations made with the trial centre. The suitability of the Investigator's co-workers, technical facilities and availability of eligible patients at the trial centre must be ensured as well as the supply and the storage of the drug. When making the appointment for the initiation visit, it will be pointed out that all those who are involved in the study at the trial centre should be present. This visit involves a detailed presentation of the study documents and discussion of unanswered questions. The Investigator must ensure that the entire study information is passed on continuously to all those who are

involved. The UoSCTU must be informed immediately of any change in the persons involved in the conduct of the study.

The study will be monitored and audited in accordance with UoSCTU procedures. All trial related documents will be made available on request for monitoring and audit by UoSCTU staff, UHS, REC and for inspection by the MHRA or other relevant bodies. Prior to the study start, the Investigator will be advised of the anticipated frequency of the monitoring visits. The Investigator will receive reasonable notification prior to each monitoring visit.

It is the duty of the Clinical Trial Coordinator (CTC) to review study records and compare them with source documents, discuss the conduct of the study and the emerging problems with the Investigator, check that the drug storage, dispensing and retrieval are reliable and appropriate and verify that the available facilities remain acceptable.

At the final close-down visit, the UoSCTU has to clarify any open questions, verify that all data requested and corrections have been entered correctly on the CRFs and collect the study material that is no longer required. All the unused drug supplied will be returned to the co-ordinating investigator.

12.4 SOURCE DOCUMENT VERIFICATION

The Investigator will allow the UoSCTU direct access to relevant source documentation for verification of data entered onto the CRFs taking into account data protection regulations. Entries in the CRF will be compared with patients' medical records and the results will be documented in the monitoring report form. Access should also be given to trial staff and departments (i.e. pharmacy).

The patients' medical records, and other relevant data, may also be reviewed by appropriate qualified personnel independent from the UoSCTU appointed to audit the study, and by regulatory authorities. Details will remain confidential and patients' names will not be recorded outside the hospital.

12.5 STUDY REPORT

At appropriate intervals, interim data listings will be prepared to give the Investigator the possibility to review the data and check the completeness of information collected. All clinical data will be presented at the end of the study on final data listings. A study report will be prepared based on the final data listings. The report will be submitted to the Investigator for review and confirmation it accurately represents the data collected during the course of the study.

12.6 RECORD RETENTION

The Investigator must maintain adequate and accurate records to enable the conduct of the study to be fully documented and the study data to be subsequently verified. After study closure the Investigator will maintain all source documents, study related documents and copies of the CRFs and Data Clarification Forms. The UoSCTU, Cancer Sciences Division, University Hospital Southampton NHS Foundation Trust /University of Southampton will maintain sponsor specific study related documents and the original CRFs. The CI will maintain specific study related documents and the original CRFs. All source documents will be retained for a period of fifteen (15) years following the end of the study.

APPENDIX 1: PAIN ASSESSMENT TOOL IMMEDIATELY AFTER VACCINATION

Anti-WT1 DNA vaccination – assessment immediately post vaccination

Partic	ipant T	rial ID		/	/		Part	ticipant	Initials			
Please mark the circle (as appropriate) below to show how intense your pain is. A zero (0) means no pain and ten (10) means extreme pain.												
How severe is your pain or discomfort now ?												
0 No pain	1	2	3	4	5	6	7	8	9 10 Extreme pa	in		
How se	vere was	your pa	in or disc	comfort c	luring an	d immed	iately aft	ter the inj	ection?			
0 No pair	1	2	3	4	5	6	7	8	9 10 Extreme pa	in		
Now plo	ease use	the sam	e metho	d to desc	ribe how	distress	i ng your	pain or di	scomfort is.			
0 No pair	1	2	3	4	5	6	7	8	9 10 Extreme pa	in		
How di s	stressing	is your p	oain or di	iscomfor	t now ?							
0 No pair	1	2	3	4	5	6	7	8	9 10 Extreme pa	in		
How dis	stressing	was you	r pain or	discomf	ort durin	g and imi	mediatel	y after th	e injection?			
0 No pair	1	2	3	4	5	6	7	8	9 10 Extreme pa	in		

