2.2 SECONDARY ENDPOINTS

2.2.1 CML:

- 1) Molecular response of BCR-ABL (major response or CMR, as defined in Section 9.6).
- 2) Molecular response of WT1 (major or minor response or CMR, as defined in Section 9.6).
- 3) Time to disease progression. Disease progression for CML patients is defined as a loss in complete haematological response, where at least one factor falls out of the following ranges (81):
 - WBC < 10×10^9 /L
 - Basophils < 5%
 - No myelocytes, promyelocytes, myeloblasts in the differential
 - Platelet count < 450 x 10^9 /L

- Spleen nonpalpable
- 4) Time to next treatment. A next treatment is defined as the first drug taken during the course of the study with an indication to treat CML.
- 5) Duration of molecular response:
 - a. Measured from the beginning of tyrosine kinase inhibitor treatment.
 - b. Measured from the time of obtaining informed consent
- 6) Overall survival.
- 7) Toxicity assessed according to NCI CTCAE v4.0.
- 8) Pain assessment immediately after vaccination
- 9) Pain assessment at 48 hrs post vaccination

2.2.2 AML:

- 1) 2 year overall survival
- 2) 2 year progression free survival.
- 3) Overall survival.
- 4) Molecular response of WT1 (major or minor response or CMR, as defined in section 9.6).
- 5) Toxicity assessed according to NCI CTCAE v4.0
- 6) Pain assessment immediately after vaccination
- 7) Pain assessment at 48 hrs post vaccination

2.2.3 HLA A2 positive patients only (CML and AML):

- 1) Immune response to WT1-epitope specific T cells in blood and/or bone marrow, using validated assays by ELISPOT and/or ICS and tetramer staining. A positive response using the validated assays by ELISPOT is defined in Section 9.6.
- 2) Number of WT1 specific T-cells after peptide challenge to the skin (wherever assessment is feasible).
- 3) Immune response to DOM, using validated assays by ELISA.
- 4) Immune response to DOM specific T cells, using validated assays by ELISPOT.
- 5) Number of humoral responses (B-cells) to the vaccine components, by ELISA.

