7.1.3 ASSESSMENT OF PAIN AND DISCOMFORT POST INJECTION

For all patients pain or discomfort and level of distress will be assessed 1 hr after injection (or after recovery from sedation) and at 48 hrs. The information will be collected, using a questionnaire (see Appendix 1 & 2).

7.1.4 PAIN MANAGEMENT AFTER VACCINATION:

The following are suggested for pain control after evaluation of the pain using the pain evaluation tools in Appendix 1 & 2:

Mild pain/discomfort - 1-4	No intervention
Moderate pain - 5-6	Paracetamol 1 g qds
Severe Pain - 7-10	Co-codamol 30/500 2 tabs qds +/- Ibuprofen 400 mg qds

Patients will be offered paracetamol to take home and will be reviewed early if severe pain occurs.

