9.3 EVALUATIONS DURING AND AT THE END OF THE STUDY

HLA Status: Registratio	n
Visit 0: Baseline (once	
Visit 1: week 0	within 7 days of baseline visit
Visit 2: week 2	14 days after v1 +/- 3 days (Not done for HLA A2 negative patients)
Visit 3: week 4	14 days after v2 +/- 7 days
Visit 4: week 8	28 days after v3 +/- 7 days
Visit 5: week 10	14 days after v4 +/- 3 days (Not done for HLA A2 negative patients)
Visit 6: week 12	14 days after v5 +/- 7 days
Visit 7: week 16	28 days after v6 +/- 7 days
Visit 8: week 20	28 days after v7 +/- 7 days
Visit 9: week 22	14 days after v8 +/- 3 days
Visit 10: week 24-28	14-42 days after v9 +/- 14 days
Visit 11: week 32	56-28 days after v10 (depending on date of v10) +/- 14 days
Visit 12: week 34	14 days after v11 +/- 3 days
Visit 13:	11 months after baseline +/- 14 days
Visit 14:	14 months after baseline +/- 14 days
Visit 15:	17 months after baseline +/- 14 days
Visit 16:	14 days after visit 15 +/- 3 days
Visit 17:	20 months after baseline +/- 14 days
Visit 18:	23 months after baseline +/- 14 days
Visit 19:	24 months after baseline +/- 14 days
Visit 20:	27 months after baseline +/- 14 days
Visit 21:	30 months after baseline +/- 14 days
Visit 22:	33 months after baseline +/- 14 days
Visit 23:	36 months after baseline +/- 14 days
After Visit 23, month 3	6, follow-up outcomes should continue to be recorded.

If delays occur on vaccination visits, all subsequent visits will be slipped to keep the interval between vaccinations at 1 and 3 months, respectively. The day 14 post vaccination visits (v2, v5, v9 and v12) should be kept as close to 14 days as possible, allowed +/- 3 days.

Investigations required at each visit:

- FBC and differential blood count, ESR
- Biochemistry
- CK test (HLA A2 positive patients only)
- Urine analysis (HLA A2 positive patients only)

- Immunological monitoring*; 65 ml of anticoagulated blood (Lithium Heparin Tubes) and 5 mL clotted blood for serum will be taken for this purpose. (Blood should be taken prior to vaccine being administered).

Investigations required at visits 1, 2, 3, 4, 6, 7, 8, 11, 13, 14, 15, 17 and 18:

- Height and weight
- Physical examination
- WHO performance status
- Vital signs

HLA A2 positive patients only - Additional investigations required after each vaccination*(Visits 1, 3, 4, 6, 7, 8, 11, 13, 14, 15, 17 and 18):

- ECG
- Echocardiogram (if clinically indicated)
- Assessment of pain and discomfort of vaccination sites

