APPENDIX 2: PAIN ASSESSMENT TOOL AT 48 HRS POST VACCINATION

Anti-WT1 DNA vaccination – Assessment at 48 hrs post vaccination

Participant Trial ID /	/ Participant Initials	
Injection type (please circle)	DNA alone / DNA+Electroporation	
Week		
Vaccination dose		
Vaccination date	d d / m m / y y	

1. Throughout our lives, most of us have had pain from time to time (such as minor headaches, sprains, and toothaches). Have you had pain other than these every-day kinds of pain today?

Yes 🗌	No		
-------	----	--	--

2. Please mark an X next to the areas where you feel pain.

Injection site	
Left arm	
Right arm	
Left leg	
Right leg	
Trunk	
Other (please specify)	

3. Please rate your pain by circling the one number that best describes your pain at its worst in the last 48 hours.

0	1	2	3	4	5	6	7	8	9	10
No										Worst pain
Pain										imaginable

4. Please rate your pain by circling the one number that best describes your pain at its least in the last 48 hours.

0	1	2	3	4	5	6	7	8	9	10
No										Worst pain
Pain										imaginable

5. Please rate your pain by circling the one number that best describes your pain at its average in the last 48 hours.

0	1	2	3	4	5	6	7	8	9	10
No										Worst pain
Pain										imaginable

6.	Please rate your pain by circling the one number that best describes how much pain you have
right N	OW.

0 No Pain	1	2	3	4		5	6	7	8	9	10 Worst pain imaginable
7.	What	treatme	ents have	e you h	ad for	your p	oain in th	ne last 48	8 hours?		
8. Please									s or med you have		provided?
0% No re	10% lief	20%	30%	40%	% 5	0%	60%	70%	80%	90%	100% Complete relief
9. you:	Circle	the one	number	that d	lescrib	es how	v, during	the past	t 48 hour	s, pain h	as interfered with
Gener	ral Activi	ity									
0	1	2	3	4	5	6	7	8	9	10	
Does I	not inter	fere at a	all						Со	mpletely	interferes
Mood	l										
0	1	2	3	4	5	6	7	8	9	10	
Does I	not inter	fere at a	1 						Со	mpletely	interferes
Walki	ng Abilit	ÿ									
0	1	2	3	4	5	6	7	8	9	10	
Does I	not inter	fere at a	111						Со	mpletely	interferes
Norm	al Work	(include	es both v	vork ou	utside	the ho	me and	housewo	ork)		
0	1	2	3	4	5	6	7	8	9	10	
Does I	not inter	fere at a	111						Со	mpletely	interferes
Relati	ons with	n other p	people								
0	1	2	3	4	5	6	7	8	9	10	
Does I	not inter	fere at a	1 						Со	mpletely	interferes
Sleep											
0	1	2	3	4	5	6	7	8	9	10	
	not inter										interferes
Fniov	ment of	life									
0	1	2	3	4	5	6	7	8	9	10

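### The three distress items in Appendix 1 carry pain-intensity anchors, and a 48-hour pain score in Appendix 2 cannot be tied to the vaccination site when several areas hurt

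*Protocol*

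**What the plan says.** Section 2.2 lists two pain assessments as secondary endpoints in both the CML and the AML cohort: one straight after vaccination, and one worded "Pain assessment at 48 hrs post vaccination". Neither names a body site, and neither mentions distress.

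Section 7.1.3 says what the forms must capture: "pain or discomfort and level of distress will be assessed 1 hr after injection", and again at 48 hours, using Appendices 1 and 2. The row for this assessment in the HLA A2 positive schedule also lists distress beside pain and discomfort, and it is marked at baseline as well as at the vaccination visits. Section 9.3 describes the task after each dose as "Assessment of pain and discomfort of vaccination sites".

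Appendix 1 opens with an intensity instruction, "Please mark the circle (as appropriate) below to show how intense your pain is", and then fixes the end points: "A zero (0) means no pain and ten (10) means extreme pain". Five scales follow. Two ask about severity and three about distress. The distress block tells the patient to answer in the same way as before.

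Appendix 2 starts with a general screening question, "Have you had pain other than these every-day kinds of pain today". Item 2 is a location list: "Please mark an X next to the areas where you feel pain", with boxes for injection site, each limb, trunk and other. Items 3–6 take the worst, least, average and current rating; item 3 reads "Please rate your pain by circling the one number that best describes your pain at its worst in the last 48 hours".

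**The concern.** A rating scale gets its meaning from its stem and its end labels together. In the distress block the two disagree: the stem asks about distress while the labels describe pain. A patient whose pain is moderate but not troubling must either choose 0, which the form labels as having no pain, or choose a number that reflects intensity. How patients resolve the conflict will vary and is not recorded. The protocol asks for distress as a separate quantity, and the form does not collect it cleanly.

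The second matter is attribution. Section 9.3 is about the vaccination sites, but the 48-hour intensity items are about the patient's pain as a whole. HLA A2 negative patients have no pain row in their schedule, so the control group supplies no estimate of background pain.

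At stake is how tolerability is described for a delivery method that section 1.8.3 itself calls painful, and for which section 7.1.2 reports experience only in healthy volunteers and 32 prostate cancer patients.

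**Working it through.** The protocol gives no figure to reproduce here. The check is a count of printed items against stated purposes.

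**Appendix 1 (immediate form)**

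| Scale | Asks about | Time frame | End labels | Labels fit the question? |
|---|---|---|---|---|
| 1 | severity | now | pain | yes |
| 2 | severity | at and just after injection | pain | yes |
| 3 | distress | none stated | pain | no |
| 4 | distress | now | pain | no |
| 5 | distress | at and just after injection | pain | no |

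- Distress scales with pain labels: 3 of 3. As a share of the form: 3 of 5.
- Severity scales with the wrong labels: 0 of 2.
- Scale 3 asks in the present tense with no time given, and scale 4 asks the same thing for the present moment. The two severity questions have no such extra item.
- The sentence defining 0 and 10 is correct where it stands, above the severity items. The fault is its reuse for distress.

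**Appendix 2 (48-hour form)**

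- Intensity ratings limited to the vaccination site: 0 of 4 (items 3–6).
- Item 2 has an injection-site box, so there are three cases:
  1. Only injection site marked: items 3–6 can be read as site pain.
  2. Injection site not marked: the ratings concern pain elsewhere.
  3. Injection site and at least one other area marked: a single number covers all of them and cannot be divided.
- Attribution therefore fails in case 3. The protocol gives no figure for how often case 3 will occur.
- Whether the injection site hurts at all can be tabulated from item 2 in every case.
- Section 7.1.3 names distress at 48 hours too, but Appendix 2 has no distress scale.

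**Reference level.** The schedule marks a baseline pain assessment in HLA A2 positive patients. Items 3–6 refer to the preceding 48 hours and not to an injection, so as printed they could be answered at baseline and serve as a within-patient reference.

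**The case against.** The strongest reply is that the endpoints in section 2.2 are pain endpoints. Distress is not among them and no site is specified. The two severity items in Appendix 1 are correctly labelled and supply the immediate endpoint in full. Each distress question states plainly what it is asking, and nothing in the protocol shows that patients would ignore the question and follow the labels. For the 48-hour form, item 2 already identifies injection-site pain, and local reactions are captured separately by site examination (section 6.4.2) and by toxicity grading and CK (section 7.1.2). Section 1.9 says that safety monitoring follows earlier protocols. Appendix 2 still asks whether DNA was given alone or with electroporation, which suggests a form carried over from a previous study. Rewording it widely could cost comparability with that experience.

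Most of this stands. It rules out a reading that the forms fail in their purpose altogether, and it argues for changing little in Appendix 2. It does not answer the labelling point: section 7.1.3 and the schedule ask for distress alongside pain, and the printed scales mislabel it.

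Three stronger inferences are tempting but unsupported:

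- **Marrow sampling at weeks 24–28 contaminates the 48-hour scores.** By the section 9.3 windows, visit 9 is at least 14 − 3 = 11 days after the week 20 dose, and visit 10 is at least 14 − 14 = 0 days after visit 9. The marrow is thus at least 11 days after that dose. The week 32 visit is at least 28 − 14 = 14 days after visit 10. The marrow falls in no 48-hour post-vaccination window.
- **A large count of spoiled ratings.** (32 + 39) × 12 = 852 forms and 852 × 3 = 2,556 distress ratings is a ceiling for 71 patients who all receive every dose. Section 4.4 stops vaccination on progression, and section 1.1.3 expects 60–75% of AML patients to relapse within 2 years.
- **A floor on 48-hour pain set by unrelated pain.** The protocol gives no background rate, and any assumed value (20%, say) would set a floor only if item 2 were ignored.

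**Conclusion.** The concern holds in a limited form. All three distress items in Appendix 1 have the wrong end labels and one is a near-duplicate without a time frame, so distress is not cleanly measured as section 7.1.3 and the schedule intend. This rests on the printed form alone. The extent to which answers would be distorted is unknown and is not claimed.

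Secondarily, sections 9.3 and 2.2 and Appendix 2 do not agree on whether the 48-hour score means vaccination-site pain or pain anywhere. The score is unattributable only for patients who mark the injection site together with another area.

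The immediate pain-severity data are sound. No primary endpoint, sample size or decision rule is affected. This is a minor, inexpensive improvement.

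**What to change.** 1. **Appendix 1.** Label the distress scales from *not at all distressing* to *extremely distressing*, and remove the untimed distress scale, keeping the two with a stated time. Leave the severity items as they are.
2. **Appendix 2 and section 2.2.** Choose one of two courses and make section 9.3 agree:
   - ask item 3 (worst pain) about the vaccination site(s), leaving items 4–6 and 9 unchanged to preserve comparability with earlier use of the form; or
   - state that the 48-hour endpoint is pain anywhere, report injection-site pain separately from item 2, and use the scheduled baseline assessment as the within-patient reference.

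The second course needs no change to the ratings in Appendix 2. The first gives a direct site score, but that score has no baseline counterpart and loses some comparability. Section 7.1.4 also draws on these forms, so the sponsor should check that any rewording is consistent with it.

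The cost is one reprinted form, or two under the first course, and a short protocol edit. Distress ratings already collected on the old Appendix 1 cannot be converted and should be reported apart from those on the new one, so the change is best made before data accumulate.
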